6.1.1.2. Rilpivirine Tablets (RPV)

RPV is provided by Janssen Research & Development, LLC, a division of Janssen Pharmaceuticals, as 25 mg tablets that are off-white, round, biconvex, film-coated and debossed on one side with "TMC" and the other side with "25". RPV is manufactured by Janssen-Cilag S.p.A, Latina, Italy. RPV will be provided as a globally marketed product which includes approvals in the US and Europe. RPV will be overlabeled and packaged in bottles of 30 tablets. The recommended storage conditions, and expiry date where required, are stated on the product label.

Each tablet contains 27.5 mg of rilpivirine hydrochloride, which is equivalent to 25 mg of RPV. Each tablet also contains the inactive ingredients croscarmellose sodium, lactose monohydrate, magnesium stearate, polysorbate 20, povidone K30 and silicified microcrystalline cellulose. The tablet coating contains hypromellose 2910 6 mPa.s, lactose monohydrate, PEG 3000, titanium dioxide and triacetin.

6.1.1.3. Cabotegravir Injectable Suspension (CAB LA)

CAB LA (GSK1265744 LA) is manufactured by GlaxoSmithKline and is a sterile white to slightly pink suspension containing 200 mg/mL of GSK1265744 as free acid for administration by intramuscular (IM) injection. The product is packaged in a glass vial with a 13 mm stopper and aluminum seal. Each vial is for single-dose use containing a withdrawable volume 3.0 mL (600 mg) and does not require dilution prior to administration. The recommended storage conditions, and expiry date where required, are stated on the product label.

CAB LA is composed of cabotegravir free acid, polysorbate 20, polyethylene glycol 3350, mannitol, and water for injection.

6.1.1.4. Rilpivirine Injectable Suspension (RPV LA)

RPV LA (TMC278, also named JNJ-16150108-AAA), 300 mg/mL Extended Release Suspension for Injection (G001), is provided by Janssen Research & Development, LLC, a division of Janssen Pharmaceuticals, as a sterile white suspension containing 300 mg/mL of RPV as the free base. The route of administration is by intramuscular (IM) injection. RPV LA is packaged in a single use 4 mL glass vial with a 13 mm stopper and aluminum seal. Each vial contains a nominal fill of 3.0 mL (900 mg), and does not require dilution prior to administration. The recommended storage conditions, and expiry date where required, are stated on the product label.

RPV LA is composed of RPV free base, poloxamer 338, sodium dihydrogen phosphate monohydrate, citric acid monohydrate, glucose monohydrate, sodium hydroxide, water for injection.

6.1.1.5. CAB LA Packs

CAB LA may be packaged in a pharmacy pack or provided in separate components:

- 3mL fill of CAB LA vial
- Vial adapters, used to draw IP out of the vials into the injection syringes
- Syringes
- Needles (23-gauge, 1.5 inch)
- Printed instructions for use

6.1.1.6. RPV LA Packs

RPV LA may be packaged in a pharmacy pack or provided in separate components:

- 3mL fill of RPV LA vial
- Vial adapters, used to draw IP out of the vials into the injection syringes
- Syringes
- Needles (23-gauge, 1.5 inch)
- Printed instructions for use

6.2. Preparation/Handling/Storage/Accountability

- The investigator or designee must confirm appropriate temperature conditions have been maintained during transit for all study intervention received and any discrepancies are reported and resolved before use of the study intervention.
- Only participants enrolled in the study may receive study intervention and only authorized site staff may supply or administer study intervention. All study interventions must be stored in a secure, environmentally controlled, and monitored (manual or automated) area in accordance with the labeled storage conditions with access limited to the Investigator and authorized site staff.
- In accordance with local regulatory requirements, the investigator, institution, or the head of the medical institution (where applicable) is responsible for study

intervention accountability, reconciliation, and record maintenance (i.e. receipt, reconciliation and final disposition records). The amount of IP dispensed and/or administered to study participants, the amount returned by study participants, and the amount received from and returned to GSK must be documented.

- Further guidance and information for the final disposition of unused study intervention are provided in the Study Reference Manual.
- Under normal conditions of handling and administration, study intervention is not expected to pose significant safety risks to site staff. Take adequate precautions to avoid direct eye or skin contact and the generation of aerosols or mists. In the case of unintentional occupational exposure notify the monitor, Medical Monitor and/or GSK study contact.
- A Material Safety Data Sheet (MSDS)/equivalent document describing occupational hazards and recommended handling precautions either will be provided to the investigator, where this is required by local laws, or is available upon request from GSK.
- Product accountability records must be maintained throughout the course of the study.

IP accountability will be evaluated using pill counts of unused IP for participants receiving oral treatment (oral CAB and oral RPV). This assessment will be conducted each time the participant receives a new (refill) supply of IP through the withdrawal or study completion.

IP accountability for participants receiving CAB LA + RPV LA will be performed at the 'vial' level (e.g., correct number of vials were used for each injection). There may be a small amount of solution remaining in the vial which does not require quantification. Used vials may be discarded at the site once accountability is complete.

6.2.1. Dosing Considerations for CAB LA + RPV LA

Vials of CAB LA and RPV LA are each supplied as a suspension and need no further dilution or reconstitution. Since RPV LA requires refrigeration, sites should allow the vial(s) to come to approximately room temperature prior to injecting. The vials should be gently inverted a few times to re-suspend sediments and allow bubbles to subside, and then use a syringe or provided vial adapter to withdraw the required volume of suspension for IM injection.

All injections must be given intramuscularly in the gluteus medius. Sites may use their discretion as to where in the gluteus muscle each injection is given according to individual participant circumstance. If possible, injections should be spaced approximately 2 cm from one another, from the site of any previous injection or any injection site reaction. The time and location of injection will be captured in the eCRF.

Intermuscular injections should be administered at a 90-degree angle into the gluteus medius muscle using a needle of appropriate gauge and length (In most participants, a 1.5" 23-gauge needle for CAB LA and a 1.5" 23-gauge needle for RPV LA is recommended). The needle should be long enough to reach the muscle mass and prevent

study drug from seeping into subcutaneous tissue, but not so long as to involve underlying nerves, blood vessels, or bone. Variable needle lengths and/or needles with different gauge (CAB LA: 21 to 25-gauge; RPV LA: 21 to 23-gauge) are permitted if needed to accommodate individual body types. Longer needle lengths may be required for participants with higher body mass indexes (BMIs, example > 30), to ensure that injections are administered intramuscularly as opposed to subcutaneously. BMI, needle gauge and length used will be collected in the eCRF. Additional details of the injection device used by sites for IM administration including, but not limited to functional performance (ie patient study participant's body position at the time of administration, etc) may also be collected within the eCRF.

At the first dose (injection), participants transitioning from oral CAB + RPV should be dosed with the IM regimen within 2 hours taking the last oral regimen dose where possible.

Additional dosing instructions and considerations can be found in the SRM.

6.3. Measures to Minimize Bias: Randomization and Blinding

For drug distribution purposes, the study will be single-arm, open-label study where all patients who pass screening will be assigned to CAB LA + RPV LA regimen.

For the purposes of implementation science/strategy, this study will be a two-arm study and sites will be either randomized to the Enhanced or Standard implementation strategy.

Cluster randomization will be applied because:

- Evaluation of intervention will be implemented at site level.
- For logistical convenience, and to avoid any contamination that could occur if implementation science interventions were provided for some subjects and not others within each site

Cluster randomization will be used to randomize sites in each country to either arm-e or arm-s. To achieve balanced implementation strategies across the sites, randomization may be stratified by clinic features. This will ensure data can identify whether a certain implementation strategy performs differently within a country or not, as well as between different countries.

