2. INTRODUCTION

2.1. Study Rationale

Cabotegravir long-acting + rilpivirine long-acting (CAB LA + RPV LA) is an investigational HIV-1 treatment regimen administered as two individual intramuscular injections every two months (following an oral lead-in [OLI] period).

The overall objective of the CAB LA + RPV LA clinical development program is to develop a highly effective, well-tolerated, two-drug, long-acting injectable regimen which has the potential to offer improved treatment convenience, compliance and improved quality of life for people living with HIV (PLHIV) compared to current standard of care.

This new HIV treatment will require changes to the current standard of prescribing oral antiretroviral therapies to prescribing and delivering a complete antiretroviral long-acting injectable regimen. As this is a new treatment modality, it is important to understand how to optimize the delivery of CAB LA + RPV LA from a patient, healthcare provider and healthcare system perspective in order to implement into routine care with fewer obstacles. Each country's healthcare system has its own challenges and nuanced differences in the delivery of HIV care. Strategies to support the unique and dynamic contexts for CAB LA + RPV LA implementation is key. As a result, this research study will examine different implementation strategies in different clinics settings across European countries to identify which strategies best meet the needs in each local context. The research in this study will involve both patients receiving the study treatment CAB LA + RPV LA (patient study participants, PSP) as well as the healthcare providers at the investigator site level (staff study participants, SSP).

For PSPs, the study is single-arm, unblinded and interventional, where all patients who fulfil eligibility requirements will be assigned to receive CAB LA + RPV LA and complete assessments as per the study protocol.

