For SSPs, the study is two-arm, unblinded, non-interventional and cluster-randomized at the country level. Sites within a given country will be randomized to either the Standard (Arm-s) or the Enhanced (Arm-e) implementation arm. The two arms will involve the provision of overlapping but distinct types of implementation components that are designed to assist in the local implementation of the study drug at each site. Arm-s represents the traditional provider support by a medical science lead and product materials. Arm-e models a higher level of provider support with added face to face meeting, trainings, and additional touchpoints for administration of CAB LA + RPV LA. The study will evaluate both qualitative and quantitative measures across arm, clinic type, provider type, and country to determine the most effective implementation strategies and to identify barriers and facilitators (including solutions). Clinical data will be collected to monitor safety and efficacy.

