4.3. Treatment Groups and Duration

4.3.1. Study sites

Investigational sites or investigators that have not previously delivered the CAB LA + RPV LA regimen will be preferred for this study. Selection will be based on ability to recruit the desired number of study participants, clinic size, demographics, geographic diversity, and patient population. Sites will be selected in order to cover a wide variety of HIV care settings. Sites will be asked to operate through their regular clinic pathways rather than a research pathway wherever possible.

Sites will be classified by the sponsor based on care delivery systems such as (but not restricted to) the following:

- Hospitals
- AIDS Reference Centers
- Hospital-based ID clinics
- Community Traveling Clinics (ex. district nurses)
- Community-based
- Sexual Health Clinics

Clinics that include participants from multiple categories (public/private) will be categorized based on the Principal Investigator's determination of most of their patient base. Each clinic selected will be categorized by country, archetype (defined above), number of providers/ staff, number of patients, and other clinical characteristics that may be considered confounders or influence implementation.

Number of Sites:

Sites across the following countries: France, Spain, Netherlands, Germany and Belgium will be selected. Exact site number will be based on feasibility assessments and approximately18 sites will be selected.

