9.2. Sample Size Determination

The study size is based on practical considerations in terms of feasibility of enrolling an adequate number of sites on each implementation strategy balanced with the desire to have interventions tested across several types of investigative sites; as well as enrolling an adequate number of patient study participants in each site.

Approximately 24 sites (from feasibility process) will be selected from the feasibility process to achieve 18 sites randomly assigned to study implementation strategies and approximately 54 evaluable staff study participants for an estimated total of 27 evaluable study staff participants per implementation strategy group.

Assuming 10% screen failures, it is estimated that with 18 sites approximately 527 patient study participants will be screened to achieve 474 subjects enrolled and 450 evaluable patient study participants completing the study (assumes 5% of patient study participants would be non-evaluable) for an estimated total of 225 evaluable patient study participants per implementation strategy group.

Power to Show Superiority in mean SSP AIM/IAM/FIM scores

Table 10 shows preliminary AIM/IAM/FIM data from the ongoing U.S. implementation study CUSTOMIZE (209493).

	N	Mean	SD	Median	Observed Range (min-max)	Floor n (%)	Ceiling n (%)	Skewness	Kurtosis
AIM Scale (Total Sample)	24	4.39	0.61	4.13	3.25-5.00	0 (0.0%)	11 (45.8%)	-0.16	-1.58
IAM Scale (Total Sample)	24	4.45	0.59	4.50	3.25-5.00	0 (0.0%)	12 (50.0%)	-0.34	-1.39
FIM Scale (Total Sample)	24	4.32	0.71	4.25	3.00-5.00	0 (0.0%)	11 (45.8%)	-0.47	-1.09

Table 10Staff Study Participants Scores at Month 4 in CUSTOMIZE (209493)

Based on these preliminary data from CUSTOMIZE study, and the given sample size (the number of study participants), the power to detect a difference of 0.5 between the implementation arms in terms of AIM, IAM and FIM are shown in Table 11.

Table 11 Power to Detect a 0.5 Difference in AIM/IAM/FIM

Endpoint	ARM-S	ARM-E	Delta	SD	Alpha	N(S)	N(E)	Power*
AIM	4.39	4.89	0.5	0.61	0.05	27	27	84%
						36	36	93%

Endpoint	ARM-S	ARM-E	Delta	SD	Alpha	N(S)	N(E)	Power*
IAM	4.45	4.95	0.5	0.59	0.05	27	27	86%
						36	36	94%
FIM	4.32	4.82	0.5	0.71	0.05	27	27	72%
						36	36	84%

*Power calculation using two-sided t-test assuming equal variance.

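### Protocol 6.3 says the randomisation lets the data show country-specific strategy effects, but about 18 sites in five countries cannot support this for the quantitative staff scores

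*Protocol*

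**What the plan says.** Protocol 6.3 sets the allocation: "Cluster randomization will be used to randomize sites in each country to either arm-e or arm-s". It adds that stratification by clinic features may be used, and then concludes: "This will ensure data can identify whether a certain implementation strategy performs differently within a country or not, as well as between different countries".

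On size, protocol 9.2 plans "to achieve 18 sites randomly assigned to study implementation strategies and approximately 54 evaluable staff study participants", with 9 sites per arm and 3 staff per site (4 as an alternative). Protocol 4.3.1 says: "Sites across the following countries: France, Spain, Netherlands, Germany and Belgium will be selected". It gives no number of sites per country: "Exact site number will be based on feasibility assessments". The SAP overview of the study design gives 1:1 site allocation.

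Table 11 of 9.2 gives power for the pooled comparison of the two arms only. No power or precision is stated for a contrast within a country or between countries. Protocol 9.4.4 lists country among the factors by which endpoints may be analysed and gives no method.

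**The concern.** Section 6.3 presents country-level resolution as something the design guarantees. It is neither offered as an exploratory aim nor supported by any calculation. The clusters are spread so thinly over five countries that an arm contrast inside one country is largely a contrast between a few clinics. A difference in that contrast between two countries is noisier still.

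The risk is one of interpretation. A reader who relies on 6.3 could take a chance difference between clinics as evidence that a strategy works in one country and not in another. Equally, the absence of a visible difference could be read as evidence that the strategies perform alike there.

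**Working it through.** **Inputs.** From protocol 4.3.1 and 9.2 and SAP 2.3: 18 sites, five countries, 1:1 allocation, 3 staff per site. From Tables 10 and 11: SD 0.61 (AIM), 0.59 (IAM), 0.71 (FIM); assumed Arm-s means 4.39, 4.45, 4.32; observed maximum 5.00; difference 0.5; two-sided t-test at 0.05 with equal variance. The documents give no intracluster correlation (ICC), so 0 to 0.1 is assumed.

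**Step 1: reproduce Table 11.** Noncentrality = 0.5 / (SD × √(1/n1 + 1/n2)), df = n1 + n2 − 2, staff treated as independent.

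| Staff per arm | AIM | IAM | FIM | Table 11 |
|---|---|---|---|---|
| 27 v 27 | 84.0% | 86.3% | 71.9% | 84%, 86%, 72% |
| 36 v 36 | 92.9% | 94.4% | 83.8% | 93%, 94%, 84% |

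Method and inputs match, so the same method can be carried to country level.

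**Step 2: sites per country.** 18 / 5 = 3.6 on average, and 3.6 / 2 = 1.8 per arm. If sites are spread roughly evenly, the typical contrasts are 2 v 2 and 1 v 2.

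**Step 3: power within one country for 0.5, no clustering.** For AIM at 2 v 2 sites (6 v 6 staff), SE = 0.61 × √(2/6) = 0.352, noncentrality = 0.5 / 0.352 = 1.42, df = 10, power 25%.

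| Sites (staff) | AIM | IAM | FIM |
|---|---|---|---|
| 2 v 2 (6 v 6) | 25% | 26% | 20% |
| 1 v 2 (3 v 6) | 17% | 18% | 14% |
| 2 v 2 with 4 staff per site (8 v 8) | 33% | 35% | 26% |

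At 2 v 2 sites with 3 staff, the difference detectable with 80% power is 1.10 (AIM), 1.06 (IAM) or 1.27 (FIM). The room between the assumed Arm-s means and 5.00 is 0.61, 0.55 and 0.68. A difference large enough to be detected would not fit on the scale.

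**Step 4: precision with clustering, site variance pooled over all sites.** Variance of a site mean = SD² × (ICC + (1 − ICC)/3). For AIM this is 0.3721/3 = 0.124 at ICC 0 and 0.3721 × 0.4 = 0.149 at ICC 0.1. Eighteen sites in 10 country-by-arm cells leave 18 − 10 = 8 df, with t = 2.306.

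- 2 v 2 sites: 2.306 × √(0.124 × 1) = 0.81 and 2.306 × √(0.149 × 1) = 0.89. Power for 0.5 is 24% falling to 21%.
- 1 v 2 sites: the factor 1 becomes 1.5, which gives 0.99 and 1.09. Power is 18% falling to 16%.

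**Step 5: difference in arm effect between two countries.** With 2 v 2 sites in each, 3 staff per site and ICC 0, the SE grows by √2 (AIM: 0.352 × 1.414 = 0.498; df = 20). Power for a 0.5 difference in effect is 16%, 17% and 13%.

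**Step 6: could an uneven split rescue the claim?** With both arms in every country, the most concentrated split is 10 sites in one country and 2 in each of the other four (10 + 4 × 2 = 18). At ICC 0, that one country (15 v 15 staff) reaches 58%, 61% and 46%. The other four are left at 1 v 1, where arm and clinic cannot be separated. For comparison, 80% power within one country needs 25, 23 or 33 staff per arm. At 3 staff per site that is 9, 8 or 11 sites per arm in that country.

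**The case against.** The strongest case for the plan has four parts.

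- **A milder reading of 6.3.** The sentence may mean only that both arms will be present in each country, so that contrasts can be formed. That does not fit the wording, which promises that a difference in performance can be identified.
- **Mixed methods.** The local-context aims in protocol 2.1, "to identify which strategies best meet the needs in each local context" and "to determine the most effective implementation strategies", rest on interviews as well as questionnaires. This stands. A reader might infer that those aims, and their counterpart in 1.1, must also be rewritten. The documents do not support that, because qualitative country-level work does not depend on these contrasts. Interviews do not, however, add clusters to a quantitative one.
- **No country-level test is shown to be planned.** A reader might infer that the sponsor intends to test arms country by country. Protocol 9.4.1 attaches p-values to the comparison of the two arms and calls the analyses by other factors exploratory. Protocol 9.4.4 and SAP 5.4.2 make country analyses optional. The implementation analysis is in a separate plan that is not among these documents and may already treat country contrasts as descriptive. All of this stands, but no analysis plan can supply more sites.
- **More alarming figures depend on method.** Estimating variance separately inside each country gives AIM half-widths of 1.52 to 1.66 (2 v 2) and 5.5 to 6.0 (1 v 2). A reader might conclude that the intervals exceed the scale. Nothing in the documents plans that analysis, and pooling over sites gives the smaller figures above. Likewise, arm and clinic are inseparable only at 1 v 1, not in every country.

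**Conclusion.** The point holds for quantitative contrasts of staff AIM, IAM and FIM scores. Section 6.3 claims a property that the design lacks. At the average site density, power for the protocol's own 0.5 difference within a country is roughly 14% to 26%, and for a difference in effect between two countries 13% to 17%, before any allowance for clustering.

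The result rests on the protocol's SDs, 3 staff per site and a roughly even spread of sites. The spread is inferred from an average, since no country split is stated; an uneven one helps a single country at the expense of the others. The ICC is an assumption, but the conclusion already holds at zero.

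The pooled arm comparison is not affected by this point, and no planned primary analysis depends on the sentence.

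**What to change.** Replace the final sentence of protocol 6.3. State that the design estimates one average arm effect over the five countries, and that quantitative arm contrasts within or between countries are descriptive and exploratory. Where such contrasts are reported, show the number of sites per arm per country beside them and give no p-values. Carry the same statement into the separate implementation analysis plan if it is not already there.

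A hierarchical model with the arm effect varying by country is optional. With about 1.8 sites per cell it would itself estimate the between-country variation weakly.

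The cost is that one stated claim becomes less favourable, plus a column of site counts in any by-country display. Sites, recruitment and conduct are unchanged.
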